## **2.2 Safety Analysis Set**

All eyes with attempted test or control article implantation (successful or aborted after contact with the eye) will be considered evaluable for the Safety Set (SS).

The SS will be used for analysis of safety endpoints.

Safety analyses will be conducted using the SS on a treatment-emergent basis. For treatment-emergent safety analyses, eyes will be categorized under the actual test or control article implanted (or attempted to implant).

## **2.3 Pharmacokinetic Analysis Set**

Not Applicable.

## **3 Subject Characteristics and Study Conduct Summaries**

Subject characteristics and study conduct summaries include tables and listings such as a subject disposition table, demographics and baseline characteristics tables (including age, gender, race, ethnicity), listing of treatment assignment by investigator, summary of screen failures by reason and listing of subjects excluded from key analysis sets including reasons. All descriptive summary statistics will be displayed with n and % for categorical data, and with mean, median, standard deviation, number of subjects, minimum, and maximum for continuous data. Tables will be presented by treatment and overall.

Subject characteristics and study conduct summaries will be presented for the primary effectiveness analysis set and the safety analysis set. Subject characteristics and study conduct summaries for the BAS analysis set will be presented if the number of subjects excluded exceeds 10%.

## **4 Effectiveness Analysis Strategy**

A total of six hypothesis tests will be conducted to address the primary and secondary objectives of the study.

The primary (Gate 1 in Figure .4-1) will be a test of non-inferiority, tested at an alpha of 0.05.

The first and second secondary (Gate 2 in Figure .4-1) will be two tests, one of superiority and one of non-inferiority, each tested at an alpha of 0.025 for a family-wise Type I error rate controlled at 0.05. The third secondary will be a test of non-inferiority and the fourth and fifth secondary (Gates 3, 4 and 5 in Figure .4-1) will be tests of superiority at an alpha of 0.05 if both of the first and second secondary null hypotheses are rejected and at an alpha of 0.025

if only one of them is rejected. The sixth secondary objective endpoints [REDACTED] will be summarized descriptively.

## 4.1 Effectiveness Endpoints

### Primary Effectiveness

- Mean binocular uncorrected intermediate VA (60 cm) (For non-inferiority testing)

### Secondary Effectiveness

- Mean binocular uncorrected intermediate VA (60 cm) (For superiority testing)
- Mean binocular uncorrected distance VA (4 m)
- Mean binocular uncorrected near VA (40 cm)
- Mean photopic binocular defocus curve
- Mean photopic without glare binocular distance contrast sensitivity
- Mean photopic with glare binocular distance contrast sensitivity
- Mean mesopic without glare binocular distance contrast sensitivity
- Mean mesopic with glare binocular distance contrast sensitivity
- Subject satisfaction

## 4.2 Effectiveness Hypotheses

### 4.2.1 Primary Effectiveness Hypotheses

The primary objective is to demonstrate non-inferiority of the TFNT00 IOL to the 839MP IOL in mean photopic binocular uncorrected intermediate (60 cm) visual acuity (UCIVA) at Visit 4A.

The null and alternative hypotheses for the primary analysis are:

$$H_0: \mu_{\text{TFNT00VA}} - \mu_{\text{839MPVA}} \geq \Delta$$

$$H_A: \mu_{\text{TFNT00VA}} - \mu_{\text{839MPVA}} < \Delta$$

where,  $\Delta$  refers to the non-inferiority margin, set at 0.1 logMAR, and  $\mu_{\text{TFNT00VA}}$ ,  $\mu_{\text{839MPVA}}$ , refer to the mean binocular high contrast UCIVA for the test and control lenses, respectively.

#### 4.2.2 Secondary Effectiveness Hypotheses

The null and alternative hypotheses for the first, fourth and fifth secondary analysis are:

$$H_0: \mu_{\text{TFNT00VA}} \geq \mu_{\text{839MPVA}}$$

$$H_A: \mu_{\text{TFNT00VA}} < \mu_{\text{839MPVA}}$$

where  $\mu_{\text{TFNT00VA}}$ ,  $\mu_{\text{839MPVA}}$ , refer to the mean binocular high contrast UCIVA, UCNVA or UCDVA for the test and control lenses, respectively.

[figure not shown]
The null and alternative hypotheses for the second and third secondary analysis are:

$$H_0: \mu_{\text{TFNT00VA}} - \mu_{\text{839MPVA}} \geq \Delta$$

$$H_A: \mu_{\text{TFNT00VA}} - \mu_{\text{839MPVA}} < \Delta$$

where  $\Delta$  refers to the non-inferiority margin, set at 0.1 logMAR, and  $\mu_{\text{TFNT00VA}}$ ,  $\mu_{\text{839MPVA}}$ , refer to the mean binocular high contrast UCDVA or UCNVA for the test and control lenses, respectively.

Descriptive statistics will be generated for the sixth secondary objective endpoints. No hypothesis tests will be performed.

## 4.3 Statistical Methods for Effectiveness Analyses

### 4.3.1 Primary Effectiveness Analyses

The primary hypothesis will be tested by generating a two-sided 90% confidence interval based on least squares means using a repeated measures analysis of variance model. The variable 'visit' will be entered as a classification variable to avoid assumptions on the shape of the response. Two-sided 90% confidence intervals for the difference between treatment groups at each visit will be reported with Visit 4A prospectively identified as the primary time point of interest. The upper bound of the two-sided 90% confidence interval will be compared to the margin, 0.1. If the upper bound is less than the margin, the null hypothesis will be rejected and the TFNT00 IOL will be concluded to be non-inferior to the 839MP IOL for UCIVA. SAS pseudo-code for this model follows:

```
proc mixed data=uci_va order=internal noclprint;
class treatment visit subject;
model uci_va = treatment|visit / solution ddfm=kenwardroger;
repeated / type=un sub=subject(treatment);
lsmeans treatment / cl diff alpha=0.1;
run;
```

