10.1 Inclusion Criteria

Below is a list of inclusion criteria. Ocular criteria must be met in both eyes with exception to criterion 4 below.

1. Adults, 22 years of age or older at the time of surgery, of either gender or any race, diagnosed with bilateral cataracts with planned clear cornea cataract removal
2. Able to comprehend and willing to sign informed consent and complete all required postoperative follow-up procedures
3. Calculated lens power between 13.0 and 30.0 D
4. 

5. [REDACTED]

Note: Subjects with any pathology that could reduce visual potential should not be enrolled in this trial

6. Preoperative regular corneal astigmatism of < 1.00 D, in both eyes

7. Clear intraocular media other than cataract in both eyes

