15.4.2.2 Analysis Methods

For the superiority hypothesis tests, treatment group comparison for UCIVA will be made and the first secondary objective will be demonstrated if $p < 0.025$ from a repeated measures analysis of variance at a Type I error rate of 2.5%. Tests at each visit will be reported with Visit 4A (120-180 days) prospectively identified as the primary time point of interest. The two-sided 95% confidence intervals will be reported for the difference between treatment groups at each visit. For the fourth and fifth secondary objectives, superiority will be demonstrated if $p < 0.05$ (or $p < 0.025$, depending on the gatekeeping) for UCNVA and UCDVA at Visit 4A (120-180 days), respectively.

For the non-inferiority hypothesis test of UCDVA, the second secondary objective, treatment group comparisons will be tested by generating a two-sided 95% confidence interval from a repeated measures analysis of variance, with site included as a covariate, at a Type I error rate of 2.5%. The variable 'visit' will be entered as a classification variable to avoid assumptions on the shape of the response and least squares means will be used to estimate the treatment effect at each visit with Visit 4A (120-180 days) prospectively identified as the primary point of interest. The upper bound of the two-sided 95% confidence interval will be compared to the margin, 0.1. If the upper bound is less than the margin, the null hypothesis will be rejected and the TNFT00 IOL will be concluded non-inferior to the 839MP IOL for UCDVA. The two-sided 95% confidence intervals will be reported for the difference between the treatment groups at each visit.

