For the non-inferiority hypothesis test of UCNVA, the third secondary objective, treatment group comparisons will be tested by generating a two-sided 95% (or 90%, depending on the gatekeeping) confidence interval from a repeated measures analysis of variance, with site included as a covariate, at a Type I error rate of 2.5% (or 5%). The variable 'visit' will be entered as a classification variable to avoid assumptions on the shape of the response and least squares means will be used to estimate the treatment effect at each visit with Visit 4A (120-180 days) prospectively identified as the primary point of interest. The upper bound of the two-sided 95% (or 90%) confidence interval will be compared to the margin, 0.1. If the upper bound is less than the margin, the null hypothesis will be rejected and the TNFT00 IOL will be concluded non-inferior to the 839MP IOL for UCNVA. The two-sided 95% (or 90%) confidence intervals will be reported for the difference between the treatment groups at each visit.

Summaries of logMAR visual acuity will also include two-sided 90% confidence intervals. A composite visual acuity endpoint comprising binocular uncorrected visual acuity at Distance (4 m) and Near (40 cm) will be summarized as a categorical variable with the following

categories: 20/20 or better (≤ 0.04 logMAR), 20/32 or better (≤ 0.14 logMAR) and 20/40 or better (≤ 0.24 logMAR).

Defocus curves will be generated for binocular defocus data, including two-sided 90% confidence intervals, with the amount of defocus along the x-axis and logMAR VA at each defocus point along the y-axis. To examine inter-site variation in outcome, forest plots of near, intermediate and distance visual acuity will be produced by plotting the difference in means and associated standard error for each site.

Contrast Sensitivity will be scored and analyzed per contrast sensitivity unit instructions.

Responses to the satisfaction question will be analyzed as a categorical variable.

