**Figure .1-1 Study Design**

### 1.3 Randomization

Post consent, the EDC system will assign the subject number. Within 10 business days of surgery, qualified subjects will be randomized, in a 1:1 ratio, to either the TFNT00 or 839MP IOL.

Randomization will be stratified by study site to ensure a balance of study treatment allocations within each investigational site.

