Mean photopic without glare binocular distance contrast sensitivity	S	Continuous descriptive statistics of scores	AAS	Observed data only
Mean photopic with glare binocular distance contrast sensitivity	S	Continuous descriptive statistics of scores	AAS	Observed data only
Mean mesopic without glare binocular distance contrast sensitivity	S	Continuous descriptive statistics of scores	AAS	Observed data only
Mean mesopic with glare binocular distance contrast sensitivity	S	Continuous descriptive statistics of scores	AAS	Observed data only
Subject satisfaction	M	Categorical descriptive statistics	AAS	Observed data only
Subject satisfaction	S	Categorical descriptive statistics	BAS	Observed data only

[figure not shown]

M=Main analysis approach; S=Sensitivity analysis approach  
bRepeated measures analysis of variance with terms for treatment and visit

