#### 4.6 Subgroup Analyses and Effect of Baseline Factors

Subgroup analyses of the primary endpoint will be conducted to assess the consistency of treatment effect across various subgroups.

The consistency of the treatment effect for binocular UCIVA, binocular UCDVA and binocular UCNVA will be assessed descriptively using summary statistics by category of the following subgroup factors:

- Age category (<65 vs. 65 years)
- Sex (Female, Male)

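### The SAP's acuity models leave out age, a baseline value recorded for every subject; adding it is an optional gain in precision, mainly for the superiority tests

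*SAP*

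**What the plan says.** SAP 4.3.1 gives the model statement for the primary endpoint as "model uci_va = treatment|visit / solution ddfm=kenwardroger". SAP 4.3.2.1 uses the same code for the secondary tests of UCIVA, UCDVA and UCNVA and changes only the alpha level. Footnote b of SAP Table 4-2 describes the method for all six tests as "Repeated measures analysis of variance with terms for treatment and visit". No baseline variable enters any of these models.

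Age is available. SAP 3 plans "demographics and baseline characteristics tables (including age, gender, race, ethnicity"). SAP 4.6 lists "Age category (<65 vs. 65 years") as a subgroup factor, but only for descriptive summaries.

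Corneal astigmatism appears as an entry limit. Protocol 10.1, criterion 6, requires "Preoperative regular corneal astigmatism of < 1.00 D, in both eyes". The visible text does not show the value as a recorded analysis variable. Several Visit 0 steps in Protocol 12.1.1 are redacted, so it may be there.

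The SAP and protocol differ on one model term. Protocol 15.4.2.2 includes site as a covariate in the non-inferiority models for UCDVA and UCNVA, and SAP 1.3 stratifies randomisation by site. The SAP code has no site term.

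**The concern.** In a linear model of a randomised comparison, adjusting for a baseline variable that predicts the outcome leaves the estimated mean difference unbiased and reduces its residual variance. A predictor that has been collected but not used therefore leaves the confidence interval wider than it need be.

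The endpoint is uncorrected acuity. Protocol 11.1 does not describe either lens as toric, and Protocol 10.2 excludes planned refractive procedures such as limbal relaxing incisions. Corneal astigmatism within the entry limit is thus left in place and could affect the outcome. Age is another plausible predictor. Neither document quantifies either relation.

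The stake lies mostly in the three superiority tests (UCIVA, UCNVA and UCDVA). They have less spare power than the non-inferiority tests. The UCIVA superiority result also helps to set the alpha level for the third to fifth secondary objectives (SAP 4 and 4.3.2.1).

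**Working it through.** **Inputs from SAP 7 and Protocol 15.10.** 76 completers per group; common SD 0.16 logMAR; true difference 0 for non-inferiority and 0.09 logMAR for superiority; one-sided alpha 2.5% for sample size. The margin is 0.1 logMAR (SAP 4.2.1). The primary test itself uses one-sided 5% (SAP 4). Like the plan, this check treats the Visit 4A comparison as a two-sample comparison.

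**Input not in the documents.** R² is the share of outcome variance explained by age, with or without astigmatism. It is assumed to lie between 0 and 0.15.

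**Step 1: reproduce the plan's own figures.**

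- SE = 0.16 × √(2/76) = 0.0260.
- Non-inferiority, one-sided 2.5%: 0.1/0.02596 = 3.85. Power is 97.1% by the normal formula and 96.9% by noncentral t with 150 df. The plan states 98%, which is about one point higher.
- Non-inferiority at the one-sided 5% used for the primary test: 98.6%.
- Superiority at 0.09 logMAR, one-sided 2.5%: 0.09/0.02596 = 3.47. Power is 93.4% (normal) or 93.1% (t), which agrees with the stated more than 90%. A two-sided 2.5% test would give about 89%, so the one-sided reading is the one that fits the plan.

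**Step 2: apply adjustment.** The residual SD becomes 0.16 × √(1 − R²), and the SE shrinks by the same factor. For R² = 0.15, √0.85 = 0.922 and the SE is 0.0260 × 0.922 = 0.0239. The equivalent total sample for an unadjusted analysis is 152/(1 − R²). Power is by noncentral t; the loss of one or two of 150 df is ignored.

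| Assumed R² | SE | 95% half-width | Superiority power, 0.09 logMAR, 2.5% | Primary non-inferiority power, 5% | Equivalent total N |
|---|---|---|---|---|---|
| 0 | 0.0260 | 0.0513 | 93.1% | 98.6% | 152 |
| 0.02 | 0.0257 | 0.0508 | 93.6% | 98.7% | 155 |
| 0.05 | 0.0253 | 0.0500 | 94.2% | 98.9% | 160 |
| 0.10 | 0.0246 | 0.0487 | 95.3% | 99.2% | 169 |
| 0.15 | 0.0239 | 0.0473 | 96.2% | 99.4% | 179 |

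**Step 3: a smaller true difference.** The plan's superiority power assumes 0.09 logMAR, nearly the whole non-inferiority margin. For an illustrative true difference of 0.05 logMAR, superiority power is 48% at R² = 0, 50% at 0.05, 52% at 0.10 and 55% at 0.15. Adjustment helps a little here too, but it does not rescue the test.

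**The case against.** The strongest reply is that nothing is wrong. The unadjusted model is prespecified and valid, and it meets the plan's 90% power target without covariates. That stands, and it is why the point is optional.

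The second reply is that the gain is unproven. No R² appears in either document. Astigmatism is limited to below 1.00 D, and Protocol 10.2 excludes amblyopia, glaucoma and degenerative eye disorders. These limits narrow what baseline variables can explain. SAP 4.6 uses age to describe consistency of the treatment effect and does not call it prognostic. This also stands: R² could be near zero.

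Third, adjustment is not entirely without cost. SAS PROC MIXED drops records with a missing covariate, while SAP 4.5 intends to use all data from evaluable subjects and plans no imputation. Covariates chosen after an unmasked look would also be open to challenge. Both matters can be handled in the wording of the change.

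A reader might infer three stronger things that the documents do not support:

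- That precision is certainly lost. It may be; the size depends entirely on an unknown R².
- That astigmatism is already held as an analysis variable. Only the eligibility threshold is visible, and numeric capture is an assumption.
- That neither document plans any covariate. The protocol includes site in two secondary models. The missing site term in the SAP is a documented discrepancy and a separate question from the one raised here.

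**Conclusion.** The point holds as an optional improvement. The SAP models for all three acuity endpoints omit age, which is recorded for every subject before randomisation, and some precision may be lost as a result. Over the assumed R² of 0 to 0.15, superiority power at 0.09 logMAR rises by between 0 and 3.1 points (93.1% to 96.2%). Primary non-inferiority power rises by at most 0.8 points (98.6% to 99.4%). The plan is neither invalid nor underpowered against its own assumptions. The figures rest on the plan's SD of 0.16 logMAR and 76 completers per group, and on an R² that the documents do not supply. Confidence that the gain would be material is low.

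**What to change.** Before any unmasked look at the data, including the Visit 3A interim analysis:

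- In SAP 4.3.1 and 4.3.2.1, add age (continuous, in years) as a fixed covariate to the MODEL statement for UCIVA, UCDVA and UCNVA. Amend footnote b of Table 4-2 to match.
- Add preoperative corneal astigmatism, as the mean of the two eyes, only if it is held as a numeric value for all subjects. Otherwise leave it out.
- Keep the present unadjusted model as a sensitivity analysis, so that no subject is lost from the results because of a missing covariate.

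The cost is one line of code per model and matching SAP text. Age needs no new data. If the covariates explain nothing, the loss is one or two of about 150 degrees of freedom. Because the same line would be edited, the sponsor could settle at the same time whether site belongs in the model, as Protocol 15.4.2.2 states for two of the tests.

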### 4.3.2 Secondary Effectiveness Analyses

#### 4.3.2.1 Visual Acuity

For the superiority hypothesis tests, treatment group comparison for UCIVA will be made and the first secondary objective will be demonstrated if  $p < 0.025$  from a repeated measures analysis of variance. The variable 'visit' will be entered as a classification variable to avoid assumptions on the shape of the response. Tests will be conducted and two-sided 95% confidence intervals for the difference between treatment groups will be generated at each visit with Visit 4A prospectively identified as the primary time point of interest. For the fourth and fifth secondary objectives, superiority will be demonstrated if  $p < 0.05$  (or  $p < 0.025$ , depending on the gatekeeping) for UCNVA and UCDVA at Visit 4A, respectively. SAS pseudo-code for this model will be the same as for the primary effectiveness analysis with, for the first secondary objective, the change to  $\alpha = 0.05$  and for the fourth and fifth secondary objectives the change to  $\alpha = 0.05$  (if only one of the first or second secondary hypotheses is rejected) and  $\alpha = 0.1$  (if both the first and second secondary hypotheses are rejected). The multiple testing strategy is listed in more detail in Section 4.4.

For the non-inferiority hypothesis test of UCDVA, the second secondary objective, treatment group comparisons will be tested by generating a two-sided 95% confidence interval based on least squares means using a repeated measures analysis of variance model. The variable 'visit' will be entered as a classification variable to avoid assumptions on the shape of the response. Two-sided 95% confidence intervals for the difference between treatment groups at each visit will be reported with Visit 4A prospectively identified as the primary time point of interest. The upper bound of the two-sided 95% confidence interval will be compared to the margin, 0.1. If the upper bound is less than the margin, the null hypothesis will be rejected and the TFNT00 IOL will be concluded to be non-inferior to the 839MP IOL for UCDVA. SAS pseudo-code for this model will be the same as for the primary effectiveness analysis with the change to  $\alpha=0.05$ . The multiple testing strategy is listed in more detail in Section 4.4.

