**Table .4-2 Summary of Analysis Strategy for All Effectiveness Endpoints**

Endpoint	Main vs. Sensitivity Approach a	Statistical Method	Analysis Set	Missing Data Approach
Primary				
Mean binocular UCIVA for non-inferiority	M	Repeated measures ANOVA b	AAS	Observed data only
Mean binocular UCIVA for non-inferiority	S	Repeated measures ANOVA b	BAS	Observed data only
Secondary				
Mean binocular UCIVA for superiority	M	Repeated measures ANOVA b	AAS	Observed data only
Mean binocular UCIVA for superiority	S	Repeated measures ANOVA b	BAS	Observed data only
Mean binocular UCDVA for non-inferiority	M	Repeated measures ANOVA b	AAS	Observed data only
Mean binocular UCDVA for non-inferiority	S	Repeated measures ANOVA b	BAS	Observed data only
Mean binocular UCNVA for non-inferiority	M	Repeated measures ANOVA b	AAS	Observed data only
Mean binocular UCNVA for non-inferiority	S	Repeated measures ANOVA b	BAS	Observed data only
Mean binocular UCNVA for superiority	M	Repeated measures ANOVA b	AAS	Observed data only
Mean binocular UCNVA for superiority	S	Repeated measures ANOVA b	BAS	Observed data only
Mean binocular UCDVA for superiority	M	Repeated measures ANOVA b	AAS	Observed data only
Mean binocular UCDVA for superiority	S	Repeated measures ANOVA b	BAS	Observed data only
Forest plots of UCNVA, UCIVA & UCDVA	M	Plot of difference in means with SE and 90% 2-sided CIs	AAS	Observed data only
Forest plots of UCNVA, UCIVA & UCDVA	S	Plot of difference in means with 90% 2-sided CIs	BAS	Observed data only
Mean photopic binocular defocus curve	M	Defocus curves with 90% 2-sided CIs	BAS	Observed data only
Mean photopic binocular defocus curve	S	Defocus curves with 90% 2-sided CIs	AAS	Observed data only
Mean photopic without glare binocular distance contrast sensitivity	M	Continuous descriptive statistics of scores	BAS	Observed data only
Mean photopic with glare binocular distance	M	Continuous descriptive statistics	BAS	Observed data only

contrast sensitivity		of scores		
Mean mesopic without glare binocular distance contrast sensitivity	M	Continuous descriptive statistics of scores	BAS	Observed data only
Mean mesopic with glare binocular distance contrast sensitivity	M	Continuous descriptive statistics of scores	BAS	Observed data only

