#### 4.5 Handling of Missing Data

All data obtained in evaluable subjects will be used in the analysis. No imputation for missing data is planned in the analyses.

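### The REPEATED statement in SAP 4.3.1 names no visit, so a Visit 4A value without a Visit 3A row could be given the Visit 3A variance

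*SAP*

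**What the plan says.** SAP 4.3.1 gives one block of SAS code. The mean model is "model uci_va = treatment|visit / solution ddfm=kenwardroger", and the residual covariance is set by "repeated / type=un sub=subject(treatment") with nothing between REPEATED and the slash. Visit is in the CLASS and MODEL statements only.

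The prose treats visit in the same way: "The variable 'visit' will be entered as a classification variable to avoid assumptions on the shape of the response". So does the footnote to SAP Table 4-2: "Repeated measures analysis of variance with terms for treatment and visit". Neither says how the covariance matrix is indexed.

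The code has wide reach. SAP section 4 states: "A total of six hypothesis tests will be conducted to address the primary and secondary objectives of the study". For the secondary acuity tests, SAP 4.3.2.1 says "SAS pseudo-code for this model will be the same as for the primary effectiveness analysis", with only alpha changed.

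On missing data, SAP 4.5 says "All data obtained in evaluable subjects will be used in the analysis. No imputation for missing data is planned in the analyses", and Table 4-2 lists "Observed data only" for every endpoint. Neither place says whether the dataset keeps a blank row for a missed visit.

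The protocol measures the three binocular uncorrected acuities at Visits 3A and 4A only (12.1.5 and 12.1.6), so the matrix is 2×2. A subject can have Visit 4A data without Visit 3A data in two ways. One is a missed Visit 3A that could not be rescheduled within its window (12.3). The other is an early exit before Visit 3A, with the Visit 4A procedures done at the last available visit (section 6, footnote 1).

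**The concern.** An unstructured covariance is chosen so that each visit may have its own variance. That works only if the procedure knows which visit a row belongs to. With no repeated effect named, PROC MIXED takes a subject's first row as position 1 and the second as position 2. The `order=internal` option orders class levels and does not index this matrix.

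A subject whose only row is Visit 4A therefore falls in position 1, which for everyone with both visits is Visit 3A. The mean model still assigns the value to Visit 4A. Its variance, and so its weight, is taken from Visit 3A, and its residual feeds into the Visit 3A variance estimate.

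At stake is the standard error of the Visit 4A difference. Its confidence limits decide the primary non-inferiority test, and the same model serves the five secondary tests.

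**Working it through.** **Inputs from the documents.** 76 completers per group, SD 0.16 logMAR, margin 0.1, true difference 0, 5% dropout, 160 implanted (SAP section 7).

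**Assumed, not in the documents.** The Visit 3A SD, the correlation between visits (0.6), and the share of subjects with Visit 4A but no Visit 3A row.

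**1. The plan's own figure.** SE = 0.16 × √(2/76) = 0.0260. Power at one-sided 2.5% = Φ(0.1/0.0260 − 1.96) = Φ(1.89) = 97.1% (96.9% with the t distribution), against the stated 98%. Completers: 152/0.95 = 160, as stated. The planned scale is reproduced closely enough for this purpose.

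**2. Weight of one misplaced value.** Write v3 and v4 for the visit variances. A Visit-4A-only subject should contribute information 1/v4; as coded it contributes 1/v3. The weight is wrong by the factor v4/v3:
- SD 0.12 (3A) and 0.16 (4A): (0.16/0.12)² = 1.78, overweighted
- SD 0.10 and 0.16: (0.16/0.10)² = 2.56, overweighted
- SD 0.20 and 0.16: (0.16/0.20)² = 0.64, underweighted
- equal SDs: 1.00, no change

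**3. Effect on the standard error.** REML fits of the 2×2 model with treatment-by-visit means were compared with the Visit-4A-only subjects placed on v4 (visit named) or on v3 (as coded).

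With 80 per arm and 5% missing Visit 4A:

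| SD 3A / 4A | Missing 3A | Reported SE, as coded versus corrected |
|---|---|---|
| 0.12 / 0.16 | 5% | −1.1% to −1.2% (four runs, 400 to 4,000 replicates) |
| 0.10 / 0.16 | 10% | −3.6% to −3.8% (three runs, 400 to 3,000 replicates) |
| 0.20 / 0.16 | assumed | +0.6% |
| equal | assumed | practically none |

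With 76 per arm and 60 replicates per scenario, both codings being fitted to the same data:

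| SD 3A / 4A | 4A-only per arm | SE as coded | SE corrected | Change |
|---|---|---|---|---|
| 0.16 / 0.16 | 4 | 0.0258 | 0.0258 | none |
| 0.12 / 0.16 | 4 | 0.0259 | 0.0262 | −1.3% |
| 0.12 / 0.20 | 8 | 0.0308 | 0.0320 | −4.0% |
| 0.16 / 0.12 | 4 | 0.0194 | 0.0192 | +0.8% |
| 0.20 / 0.12 | 8 | 0.0200 | 0.0196 | +2.1% |

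**4. Effect on the estimate.** Mean estimates hardly differ between the codings: 0.0003 under both in the mild scenario (0.12/0.16, 5%), and −0.0009 and −0.0011 in the extreme one (0.10/0.16, 10%). In a single dataset the estimate moves by 0.003 logMAR on average in absolute value in the mild scenario (maximum about 0.02). The plan equates 0.09 logMAR with 4.5 letters, so one letter is 0.02 and the shift is 0.003/0.02 = 0.15 letter. In the extreme scenario the true sampling SD rises from 0.0251 to 0.0266 while the reported SE falls.

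**5. Error rates, as coded versus corrected, one-sided 2.5%.**
- Mild: 3.0 v 2.4, 2.3 v 2.1 and 2.7 v 2.5%. The simulation error of one rate from 2,500 replicates is √(0.025 × 0.975/2,500) = 0.3 points, so no inflation is established.
- Extreme: 3.5 v 2.3, 3.1 v 2.2 and 3.6 v 2.4%. That is 0.6 to 1.1 points above nominal and 0.9 to 1.2 points above the corrected code.

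At the primary test's one-sided 5%, one run gave 5.4 v 4.9% (mild) and another gave 6.0 v 4.7% (extreme). Non-inferiority power barely moves: 98.6 v 98.7% (mild) and 98.6 v 98.8% (extreme).

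**6. Effect on the primary limit.** With SE 0.026, a 1.2% error moves the upper 90% limit by 1.645 × 0.012 × 0.026 = 0.0005 logMAR, and a 3.8% error by 0.0016. At a true difference of 0 the limit sits near 1.645 × 0.026 = 0.043, well below 0.1.

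The two larger error-rate runs used a t reference with fixed degrees of freedom (148 and 150) rather than the Kenward-Roger adjustment in the SAP.

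**The case against.** The strongest reply is that the fault depends on things the documents leave open.

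- **Dataset layout.** If a missed Visit 3A is kept as a row with a blank response, in visit order, each value keeps its position and nothing goes wrong. A reader might infer from the observed-data rule that such rows are dropped. The SAP does not say so: it rules out filling in values and is silent on row structure. This stands, and it makes the point conditional.
- **Number of subjects affected.** The 5% dropout concerns subjects who do not complete. Someone measured at Visit 3A and then lost is placed correctly. Sites are told to reschedule missed visits. No rate of Visit-4A-only subjects can be taken from the documents.
- **Unequal variances.** The only SD given is 0.16, with none by visit. The largest effect reported at one-sided 2.5% needs a Visit 4A variance 2.56 times that at Visit 3A together with 10% missing Visit 3A. This also stands.
- **Pseudo-code.** The SAP uses that label, and the LSMEANS line must be edited in any case, because it requests treatment means over visits while the text needs Visit 4A. This stands in part. The block is still the only covariance specification in the plan, and correcting LSMEANS would leave the REPEATED line as it is.

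**Conclusion.** The omission is real, and it sits in the code that serves all six tests. Its consequence is conditional: it needs at least one subject with Visit 4A only, a dataset without a placeholder row, and visit variances that differ.

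Where all three hold, under the assumed SDs, correlation and missed-visit rates, the standard error is about 1% too small in the mild scenario and about 4% too small in the extreme one. It is too large when Visit 3A is the more variable visit. Type I error inflation at one-sided 2.5% is within simulation noise in the mild scenario and roughly 0.5 to 1.2 points in the extreme one.

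Two stronger readings are tempting and are not supported. One is that the six tests will use the wrong variance; the documents do not settle the dataset layout or the visit variances. The other is that the estimate is biased; the simulations show added scatter around essentially the same mean. The primary non-inferiority conclusion is unlikely to change. The practical exposure is a borderline superiority result. Severity is minor.

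**What to change.** In SAP 4.3.1, change the line to `repeated visit / type=un sub=subject(treatment);`. Visit is already in the CLASS statement, and 4.3.2.1 carries the change to the five secondary tests. The edit can be made together with any correction of the LSMEANS line in the same block.

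The cost is one word in the SAP and in the program. Sample size, alpha and data collection do not change. If no subject lacks a Visit 3A row, the results are identical. If some do, each Visit 4A value takes the Visit 4A variance whatever the dataset layout. It is best done before unmasking, so that the primary analysis code is not altered afterwards.
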